The above randomization scheme was specified to ultimately yield equal cell sizes for each of the four conditions (i.e., 25% of randomized subjects in each). However, as of 10/28/2019, the four cell sizes were imbalanced (ranging from 15.9% to 25%) due to a large number of CBM-I subjects not completing Session 1 after Stage 1 randomization to the CBM-I arm of the intervention. Importantly, completed Session 1 measures were needed for the attrition algorithm to be able to classify CBM-I subjects as high or low risk of dropout before Stage 2 randomization could be applied to high risk subjects. Thus, to reduce the imbalance in the number of subjects randomly assigned to each of the four groups across both stages of randomization, we changed the allocation at Stage 1 randomization on 10/31/2019 from 25% Psychoeducation and 75% to CBM-I to 10% and 90%, respectively.

Sampling Plan

Existing Data

Registration prior to analysis of the data

Explanation of Existing Data

We registered the overall project and identified primary outcomes at clinicaltrials.gov (<https://clinicaltrials.gov/ct2/show/NCT03498651>) prior to data collection. However, this pre-registration through OSF is occurring after data collection but prior to any data analysis. This pre-registration represents the first set of substantive analyses proposed in this dataset. To date, these data have only been viewed by members of the overall data collection team to ensure accurate and representative enrollment of participants (i.e., that we are succeeding in recruiting a diverse sample). We also regularly reported attrition updates by blinded condition to an independent safety monitor throughout the data collection process and completed blind data integrity checks (i.e., to catch duplicate entries). Data cleaning is currently ongoing by members of the team who are not involved in hypothesis generation.

Data Collection Procedures

Intervention sessions were administered and data were collected through the established MindTrails website. Enrollment was open to an international sample of anxious adults (inclusion

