criteria listed in the study design section of this registration). Participants were recruited through postings on online newsletters, research websites, mental health forums, Craigslist, social media (e.g., Facebook, Instagram, Twitter, Reddit), and UVA student group listservs; flyers posted in the Charlottesville community and at UVA and other nearby universities and community colleges; news sources (e.g., articles, radio interviews, podcasts); and Google Ads. In addition, to improve recruitment of underrepresented groups, we sent emails to a market research firm's database of participants who self-identified with anxiety or depression and as Black/African American, Hispanic/Latinx, or Asian; we also posted in an online newsletter for multicultural student services at UVA. Note that participants may have presented to the Mindtrails website starting on 3/12/2020 due to concerns over the developing COVID-19 pandemic. Although future analyses may choose to test whether these participants interacted with the intervention differently than did pre-COVID participants, we elect to combine all participants in this initial investigation of the major aims of this clinical trial.

Per protocol, after enrollment and informed consent was obtained, each participant completed a pre-treatment assessment battery, one training session per week over the course of five weeks, comprehensive assessment batteries immediately following training sessions 3 and 5, and a follow-up assessment battery two months after training ended. Participants also completed a shorter schedule of assessments after training sessions 1, 2, and 4 to reduce participant burden.

Participants were compensated via e-gift cards according to the following payment schedule. Participants were awarded \$5 per assessment battery completed at pre-treatment, after session 3, and after session 5. Participants were further awarded \$10 for completing the 2-month follow-up assessment, amounting to a total possible compensation of \$25 in e-gift cards distributed by Tango Cards.

No files selected

Sample Size

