Per protocol, we planned to recruit and enroll 1,000 highly anxious individuals and sequentially employ a series of weighted randomization rules to achieve four treatment arms (i.e., four study conditions) of approximately equal weight (approximately 250 participants per group). Data collection is now complete and we enrolled 1746 participants in total. Of these, 1238 started the first training session and are considered intent to treat (ITT). At Stage 1 randomization, 984 ITT participants were assigned to CBM-I, and 254 ITT participants were assigned to psychoeducation. 1075 ITT participants completed assessments immediately following the first training session (835 in CBM-I and 240 in psychoeducation) and are included in our primary analyses. The 835 CBM-I completers of the session 1 assessments were classified as higher ($n = 547$) or lower ($n = 288$) risk of study dropout, whereas the 149 CBM-I participants who did not complete the session 1 assessments were not able to be classified as higher or lower risk of study dropout. Of the 547 CBM-I participants classified as higher risk of study dropout, at Stage 2 randomization 282 were assigned to receive coaching and 265 were assigned to no change. In total, 559 of the 1238 ITT participants completed five training sessions and are deemed treatment completers.

Sample Size Rationale

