Prior to data collection, we conducted an analysis of variance (ANOVA) to estimate the sample size needed to test main effects of delivery methods (i.e., phone vs. computer), human contact, and their interaction according to a 2 (phone vs. computer) x 3 (high risk: TeleCoach, high risk: continued CBM only, low risk: continued CBM only) design. While we ultimately decided to not randomize participants to CBM-I delivery platform (to prioritize participant preference to maximize engagement and minimize burden), our initial power analysis assumed small to medium effects for this 2x3 design. In this power analysis, we elected to be conservative due to the SMART design yielding unbalanced cell sizes. Further, given that the second stage of randomization is based on performance in the earlier stage, we were unable to determine what an effect size might be in advance. With our assumed effect size ($d = .35$, $f = .175$), to have 80% power, we would need $n = 240$ to detect a main effect. However, given that we expected high rates of attrition, we assumed a 66% dropout rate (based on previous attrition rates on our MindTrails cite), so we multiplied $n = 240$ by 3 [i.e., $1/1-.66$], resulting in $N = 720$. For the psychoeducation comparison condition, we elected to match the sample size to the expected final cell size for the three other conditions (i.e., $n = 120$). We did not scale up the condition sample size given the SMART design does not split the control condition in a second stage of randomization.

Stopping Rule

We stopped data collection based on a selected date. Data collection began on 3/18/2019. We analyzed data collected through 11/27/2020.

Variables

Manipulated Variables

There were two stages of randomization throughout the SMART (described elsewhere in this pre-registration).

No files selected

Measured Variables

Interpretation Bias (Target Engagement)

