2) Depression, Anxiety, Stress Scales-Short Form - Anxiety Subscale (DASS-AS; adapted from Lovibond & Lovibond, 1995). To assess eligibility to enroll in the study and to measure participants' subjective evaluations of the frequency of their anxiety symptoms since their last training session, participants completed the seven-item DASS-AS using the response scale 0 ("not at all") to 3 ("most of the time"), where higher scores indicate greater symptom severity. Participants also had the option to select Prefer Not to Answer. Participants completed this questionnaire at pre-screener, after session 3, after session 5, and at 2-month follow-up.

No files selected

Indices

No response

No files selected

Analysis Plan

Statistical Models

Models Testing Interpretation Bias and Anxiety Symptom Hypotheses

To assess the impact of different treatment arms on interpretation bias and anxiety symptom outcomes, we will run a series of multilevel models estimated in the Bayesian framework using the rjags package in R. Due to the repeated outcome monitoring structure of this clinical trial, assessment points will be nested within individual participants. We will control for socioeconomic status and age in all models given previous evidence that these demographic characteristics are associated with differential treatment responses to CBM-I. To our knowledge, this will be the first Bayesian test of CBM-I treatment effects and is also the first CBM-I SMART design. As such, we will use uninformative priors in these estimations.

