Due to the study's SMART design, we will employ a piecewise linear function to model time. Doing so will allow us to minimize the bias that a simple linear mean trajectory would otherwise impose by not accounting for the possible deflection points at the time of re-randomization (Nahum-Shani et al., 2019). In a piecewise linear regression model, a separate line segment can be fit for different intervals over the course of the study, with the boundary for the time intervals forming a transition point, such as from one treatment stage to another. In the current study, we have three stages of interest: the first stage (S1) of the clinical trial (pre-treatment to re-randomization point after session 1); the second stage (S2) of the clinical trial (session 2 to session 5); and the third, or follow-up, stage (S3) of the clinical trial (session 5 until two months later). With a piecewise regression model, the linear trend in the outcome during the first stage can be allowed to vary from the linear trend during the second and third stages, and to be impacted by different variables. We will assume the same intercept for all four treatment arms because, by design, treatment arms are not expected to differ at baseline. We will assume that the marginal mean trajectory between the 3 CBM-I treatment arms will be equivalent until re-randomization occurs for the high-risk CBM-I participants following the first session. Given that longitudinal modeling of SMART data must accommodate features of the SMART design itself (Nahum-Shani et al., 2019), we will code time using three variables constructed in the manner outlined in Pre-registration Table 1.

Pre-Registration Table 1

Time	S₁	S₂	S₃
Pre-intervention	0	0	0
Session 1	1	0	0
Session 2	1	1	0
Session 3	1	2	0
Session 4	1	3	0
Session 5	1	4	0
2-month Follow-up	1	4	1

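### The Stage 1 allocation ratio changed mid-trial, but neither model adjusts the CBM-I versus psychoeducation contrast for allocation period

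*Combined protocol and SAP*

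**What the plan says.** The Randomization section describes a Stage 1 ratio of 75:25 (CBM-I to psychoeducation), stratified by gender and baseline anxiety severity. It then reports that "we changed the allocation at Stage 1 randomization on 10/31/2019 from 25% Psychoeducation and 75% to CBM-I to 10% and 90%, respectively". The reason given is imbalance in cell sizes, because many CBM-I participants did not complete session 1. No change to the 50:50 Stage 2 ratio is reported.

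The Stopping Rule section gives the calendar: "Data collection began on 3/18/2019. We analyzed data collected through 11/27/2020". Data Collection Procedures adds that "participants may have presented to the Mindtrails website starting on 3/12/2020 due to concerns over the developing COVID-19 pandemic", and for the present analysis "we elect to combine all participants in this initial investigation of the major aims of this clinical trial".

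On counts, Sample Size states that "984 ITT participants were assigned to CBM-I, and 254 ITT participants were assigned to psychoeducation", and that "1075 ITT participants completed assessments immediately following the first training session (835 in CBM-I and 240 in psychoeducation"; the latter set is the primary analysis set.

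On the models, Statistical Models says "We will control for socioeconomic status and age in all models". Both covariates enter the intercept and every stage slope, with interactions. It also says: "We will assume the same intercept for all four treatment arms because, by design, treatment arms are not expected to differ at baseline". The time codes S1 to S3 start at zero for each person whatever the calendar date (Transformations), so they carry no information on enrolment period. The Missing Data section lists candidate auxiliary variables; enrolment date and allocation period are not among them.

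**The concern.** Under a changing ratio, assignment is random given the ratio in force. Once the two periods are pooled, a larger share of CBM-I than of psychoeducation participants comes from the later period. The common intercept is justified by design, but after a ratio change the design supports that only conditional on period.

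If later entrants change differently on anxiety or interpretation bias, or drop out at a different rate, part of that difference appears as an effect of CBM-I. The plan itself names one possible shift: entry prompted by COVID-19 from 3/12/2020, wholly inside the 10:90 phase. The contrast at stake is the first outcome hypothesis and also one of the dropout hypotheses. A shift that acts through age or SES is already adjusted; other shifts are not.

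**Working it through.** **Inputs from the documents.** Ratios 25:75 and 10:90 (psychoeducation:CBM-I), change date 10/31/2019 (Randomization). ITT counts 984 and 254, primary-set counts 835 and 240, 1746 enrolled, 559 completing all five sessions (Sample Size). The counts add up: 984 + 254 = 1238 and 835 + 240 = 1075.

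**Assumed.** Counts by arm and period are not given. Let k be the ratio of CBM-I to psychoeducation session 1 start rates, constant over time.

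**Step 1, limits for k.**
- Upper limit: if everyone came before the change, k = 984/(3 × 254) = 1.29.
- Lower limit: no more than the 1746 enrolled can have been randomised, so 984/k + 254 ≤ 1746, giving k ≥ 984/1492 = 0.66.

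**Step 2, post-change share by arm.** The psychoeducation share among starters is a = 0.25/(0.25 + 0.75k) before the change and b = 0.10/(0.10 + 0.90k) after it. The number starting from the earlier period is x = (254 − 1238b)/(a − b).

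At k = 1: x = (254 − 123.8)/0.15 = 868, leaving 370 after the change, of whom 37 are psychoeducation and 333 CBM-I. The shares are 333/984 = 33.8% and 37/254 = 14.6%.

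| k | CBM-I after change | Psychoeducation after change | Gap (points) |
|---|---|---|---|
| 0.8 | 57.1% | 30.7% | 26.4 |
| 1.0 | 33.8% | 14.6% | 19.3 |
| 1.1 | 22.2% | 8.7% | 13.5 |
| 1.2 | 10.6% | 3.8% | 6.8 |

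The maximum is 26.8 points, at k of about 0.75. The gap shrinks to zero only at the upper limit, where nobody came after the change. If session 1 assessment completion within each arm did not differ by period, the same gaps hold in the primary set (k = 1: about 283/835 and 35/240).

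**Step 3, effect on the contrast.** Bias = gap × period difference.
- 0.1 SD: 0.193 × 0.1 = 0.02 SD at k = 1, at most 0.268 × 0.1 = 0.03.
- 0.2 SD: 0.193 × 0.2 = 0.04 SD at k = 1, at most 0.268 × 0.2 = 0.05.
- Two-group standard error: sqrt(1/835 + 1/240) = 0.073 SD. This is a yardstick, not the standard error of the Bayesian piecewise model.
- Dropout, assumed 10-point period difference: 1.9 points at k = 1, at most 2.7. With a completion proportion of 559/1075 = 0.52, the two-group standard error is sqrt(0.52 × 0.48) × 0.0732 = 3.7 points.

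**Step 4, cost of adjusting.** The standard error becomes 0.0732/sqrt(1 − r²), where r is the correlation of arm with period.
- k = 1.1: r = 0.143, SE 0.0740 (+1.0%).
- k = 1: r = 0.176, SE 0.0744 (+1.6%).
- k = 0.8: r = 0.220, SE 0.0751 (+2.5%).

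**Step 5, which terms can be estimated in the dropout model.** The text models sessions 2 to 5. In Pre-Registration Table 3, S1 equals 1 at all of these, so period and period × S1 are the same column. With P for period, the design [1, S1, S2, P, P×S1, P×S2] has rank 4 of 6, so only two period terms are estimable. Keeping the pre-intervention and session 1 rows would not help: everyone analysed completed session 1, so those rows contain no dropout.

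**The case against.** The strongest reply is that no period effect is shown. The ratio was changed because of cell sizes, not outcomes, and both k and the period difference are assumptions. For differences of 0.1 or 0.2 SD the shift stays below one two-group standard error at every feasible constant k. All of this stands, and it limits the point to a precaution.

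Second, the plan openly chose to pool over calendar time. That decision concerns COVID-era participants. It does not mention that the ratio had changed or that period is tied to arm, so it answers only part of the point. Pooling can continue with a period term in the model.

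Third, the models already absorb some shifts: age and SES are adjusted throughout, and a pure shift in level is partly taken up by the random intercept. Period differences in stage slopes or in dropout are not.

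A reader might infer that a period term would restore a fully randomised comparison. The documents do not support that. The primary set excludes 149/984 (15.1%) of CBM-I and 14/254 (5.5%) of psychoeducation ITT participants after randomisation, and the Data Exclusion section concedes that this interferes with causal claims. The period term leaves that untouched.

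**Conclusion.** The point holds as an avoidable exposure to bias in the CBM-I versus psychoeducation contrast, in both the outcome and dropout models. The gap in post-change share is 19.3 points at equal start rates and at most 26.8 over k from 0.66 to 1.29, provided k is constant over time. At k = 1, assumed period differences of 0.1 or 0.2 SD give shifts of 0.02 or 0.04 SD.

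Three stronger conclusions are not supported:
- That the contrast is biased. The documents report no period effect. Using the planned d of 0.35 as a period difference would give about 0.07 SD at k = 1, but nothing in the documents justifies that use.
- That telecoaching versus no telecoaching is affected. Its ratio was 50:50, with no reported change.
- That COVID-era participants must be removed. The Stage 1 ratio is constant within the 10:90 phase, so a single indicator suffices for this purpose.

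Adjustment is worthwhile because it is cheap and ties the contrast to the ratio actually in force. Confidence in the size is moderate, since the arm-by-period counts are not given.

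**What to change.** Add an indicator for the Stage 1 ratio in force at randomisation (before versus from 10/31/2019):

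- **Set 1:** in the intercept and in the S1, S2 and S3 slope equations (four terms). An intercept term alone would not adjust the slopes.
- **Set 2, on sessions 2 to 5:** in the intercept and the S2 slope only (two terms).

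Report the period-adjusted CBM-I versus psychoeducation contrast either as primary or beside the registered model. Where a1 and a2,1 both enter, report one combined effect, because Pre-Registration Table 2 gives them identical codes. Report counts by arm and period, and state that the adjustment does not address the exclusion of session 1 non-completers.

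The cost is one recorded date, a few extra terms, and a standard error about 1 to 2.5% larger in the two-group approximation (k from 1.1 to 0.8); the cost in the Bayesian model is not known. The post-change psychoeducation cell is small, about 21 to 74 of the 240 over the same range of k, so any by-period estimates should be combined and not read separately.

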Notably, participants were not randomly assigned to their high- or low-risk status, so causal inference between the high and low risk CBM-I groups is unsupported by this SMART design. However, we expect that participants identified as being at high risk of treatment dropout but who did not receive the telecoaching intervention will show earlier treatment dropout than CBM-I participants identified as being at low risk for attrition. As a secondary analysis, we will also compare treatment dropout between low risk CBM-I participants and those high risk CBM-I participants who received the additional telecoaching intervention to test whether or not the supplementary telecoaching intervention appears to buffer against the risk of early dropout. However, this hypothesis is non-directional.

Design Plan

Study Type

Experiment - A researcher randomly assigns treatments to study subjects, this includes field or lab experiments. This is also known as an intervention experiment and includes randomized controlled trials.

Blinding

For studies that involve human subjects, they will not know the treatment group to which they have been assigned.

Is there any additional blinding in this study?

No response

Study Design

We recruited and enrolled 1746 anxious adults with access to a smartphone, computer, or tablet to participate in a “computer-based program to reduce anxiety symptoms.” Participants were eligible to participate if they scored at or above a 10 on the anxiety subscale of the Depression, Anxiety, and Stress Scale (DASS-AS; Lovibond & Lovibond, 1995), had access to an internet-enabled device, and were at least 18 years of age.

Enrolled participants who completed readiness rulers and demographics questions at pretreatment were randomly assigned to either complete five 15-minute cognitive bias modification for interpretations (CBM-I) training sessions with 40 scenarios per session or to a psychoeducation condition according to a 75:25 stratified randomization ratio schedule. Participants were instructed to complete one training session per week over the course of five weeks and were instructed to complete these online training sessions using their preferred internet-enabled device (i.e., participants could opt to use multiple devices or to use the same device throughout the five-week training).

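### The set called intent to treat is the session 1 starters, not everyone randomized, so completion on all randomized is unknown and the CBM-I versus psychoeducation dropout comparison omits the earliest losses

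*Combined protocol and SAP*

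**What the plan says.** The Study Design section places the first randomization at pretreatment, before any training: "Enrolled participants who completed readiness rulers and demographics questions at pretreatment were randomly assigned to either complete" CBM-I training or psychoeducation.

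The Sample Size section then gives the flow of participants. It starts from enrolment: "Data collection is now complete and we enrolled 1746 participants in total". It labels the next set: "Of these, 1238 started the first training session and are considered intent to treat (ITT"). Assignment by arm is given only within that set: "At Stage 1 randomization, 984 ITT participants were assigned to CBM-I, and 254 ITT participants were assigned to psychoeducation". The set for the primary analyses is smaller again: "1075 ITT participants completed assessments immediately following the first training session (835 in CBM-I and 240 in psychoeducation"). Completion is stated as counts: "559 of the 1238 ITT participants completed five training sessions and are deemed treatment completers".

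Four other places bear on the point:

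- *Treatment Dropout Hypotheses* predicts less attrition in the three CBM-I arms than in psychoeducation.
- *Models Testing the Probability of Dropping Out of Treatment* limits the dropout model to people who finished the first training and its assessment.
- *Data Exclusion* concedes that the set of 1075 is not intent to treat and gives the reason: risk class and Stage 2 assignment are unknown for the others. It makes no such concession for the 1238.
- *Randomization* reports that many CBM-I participants did not complete session 1 after Stage 1 randomization, and that the allocation was changed for this reason on 10/31/2019 from 75:25 to 90:10. It gives no count.

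**The concern.** Intent to treat means everyone randomized, in the arm assigned. Starting session 1 happens after Stage 1 randomization, so a set defined by it cannot carry that name. The plan thus claims for the 1238 a property that they do not have, and a reader comparing the 1075 with the ITT sample would take the 1238 as the full randomized group.

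Retention is one of the trial's stated questions. Leaving between randomization and session 1 is the first form that dropout can take, and leaving during session 1 or its assessment is the second. The planned dropout model counts neither. For the telecoaching question this is proper, because that randomization happens after the session 1 assessment. For CBM-I versus psychoeducation it is not, because that assignment was made before either loss.

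**Working it through.** **Inputs.** From Sample Size: enrolled 1746; started session 1 1238 (984 CBM-I, 254 psychoeducation); completed the session 1 assessment 1075 (835 and 240); CBM-I starters without that assessment 149; completed five sessions 559. The number randomized, R, is not in the readable text.

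**1. The plan's counts agree.** 984 + 254 = 1238; 835 + 240 = 1075; 984 − 835 = 149. By the same subtraction, 254 − 240 = 14 psychoeducation starters lack the assessment, and 149 + 14 = 163 = 1238 − 1075.

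**2. People outside the set called ITT.** 1746 − 1238 = 508, and 508/1746 = 29.1% of those enrolled.

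**3. Completion by denominator.** The plan prints only 559 and 1238; the percentage is derived: 559/1238 = 45.2%. On all randomized it is 559/R, with R assumed to lie between 1238 and 1746:

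| Share of the 508 who were randomized | R | 559/R |
|---|---|---|
| 0% | 1238 | 45.2% |
| 25% | 1365 | 41.0% |
| 50% | 1492 | 37.5% |
| 75% | 1619 | 34.5% |
| 100% | 1746 | 32.0% |

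In the set that the dropout model uses, completion would be 559/1075 = 52.0%, if all 559 completers are among the 1075.

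**4. How much dropout the model does not see.** On the same assumption, starters who did not complete number 1238 − 559 = 679, and 163/679 = 24.0% of them are outside the model. If all 1746 were randomized, non-completers number 1746 − 559 = 1187, and (508 + 163)/1187 = 56.5% are outside it. The share therefore lies between 24.0% and 56.5%.

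**5. The part of the early loss that can be seen by arm.** Among starters, loss before the session 1 assessment was finished:

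- CBM-I: 149/984 = 15.1%
- Psychoeducation: 14/254 = 5.5%

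The difference is 9.6 percentage points, with the larger loss in CBM-I. The hypothesis predicts the opposite. The loss from randomization to start cannot be computed for either arm.

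**The case against.** **No planned model uses the 1238.** The primary analyses and the dropout model use the session 1 assessment completers, and the secondary analyses use treatment completers. Renaming the 1238 changes no estimate, and Data Exclusion openly gives up the ITT claim for the set that is analysed. This stands, and it limits the weight of the label. It does not answer the dropout comparison. The reason given for the exclusion is missing risk class and Stage 2 assignment, and neither is needed to compare CBM-I with psychoeducation.

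**Blinding.** A reader might infer that people chose whether to start according to their arm. The documents do not support this. The Blinding entry says that participants will not know their group, which makes different rates of non-start less likely. The remark under Randomization concerns not completing session 1, mixes starters with non-starters, and gives no figure for psychoeducation. Blinding does not repair the label or the denominator. Nor does it cover loss once session 1 has begun, when the content itself may differ noticeably.

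**The 32.0% figure.** A reader might take it as the true completion rate. It is only a bound. Randomization required completed readiness rulers and demographics questions, so some of the 508 may never have been randomized; the text does not settle how many.

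**Visibility.** The plan prints 1746 next to 1238, so the gap of 508 is in plain view. That is fair: what is missing is how many of them were randomized, and to which arm. The study-flow figures are not reproduced in the text available here, so the absence of a randomized count can be asserted only of the readable text.

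**Conclusion.** The point holds as a matter of labelling, denominator and one hypothesis. The 1238 are session 1 starters, not an intent-to-treat set. Completion is 45.2% of starters and somewhere from 32.0% to 45.2% of those randomized, depending on a count that the text does not give.

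The consequence for inference is confined to the predicted lower attrition in CBM-I than in psychoeducation. The planned model begins after the session 1 assessment, and the one earlier step visible by arm runs against the prediction, 15.1% against 5.5%. That contrast is descriptive. It pools two allocation periods, and some of the 163 may have finished the training and missed only the assessment. It does not show that CBM-I causes more dropout overall; it shows that the result could depend on where counting starts.

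The Stage 2 comparison (282 coached, 265 not) is untouched. The point should be acted on, but it does not undermine the main symptom models beyond what Data Exclusion already concedes.

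**What to change.** 1. Rename the 1238 as *session 1 starters*, and define intent to treat as everyone randomized at Stage 1.
2. State the number randomized and the number starting session 1, by arm and by allocation period (75:25 and 90:10).
3. Give five-session completion on all randomized, beside the figure for starters.
4. Beside the planned dropout model, add a CBM-I versus psychoeducation comparison of dropout on all randomized. Count non-start and non-completion of session 1 as dropout, and stratify by allocation period. Stratification is needed because the mix of arms changed on 10/31/2019, so any change in attrition over calendar time would otherwise be confounded with arm.

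The cost is a count from the existing database, one added analysis, and a completion figure that can only stay the same or become less favourable. No new data, risk class or Stage 2 assignment is needed.
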